9.4.5 Subgroup Analyses

The analyses described in [Section 9.4.3](#) will be repeated on the primary estimand only using the subgroups defined in [Section 7.2](#) for baseline disease severity and obesity. There will be no figures for the subgroup analyses.

9.5 Secondary Efficacy Analyses

The primary estimand approach will be applied to these endpoints, with the exception of the partial relapse, relapse and rebound endpoints, in the same manner as described in [Section 9.4.1](#). No additional supportive or sensitivity analyses will be applied to these endpoints, with the exception of PASI-50 response which has a supportive estimand and DLQI score which has a supportive analysis.

There will be no waterfall plots for the secondary endpoints, with the exception of absolute change from Baseline in PASI score at Week 16.

9.5.1 Percentage Change from Baseline in PASI score at Weeks 4, 8 and 12

Mean percentage change from baseline in PASI score at Weeks 4, 8 and 12 will be analysed as part of the MMRM for the primary estimand. The same statistics produced for the Week 16 time point will also be produced at Weeks 4, 8 and 12.

9.5.2 Other Continuous Secondary Endpoints

The following secondary endpoints will be analysed in the same manner as described for the main analytical approach for the primary analysis ([Section 9.4.30](#)):

- Mean absolute change from baseline in PASI score at Weeks 4, 8, 12, and 16
- Mean percentage change from baseline in LSS at Weeks 4, 8, 12, and 16
- Mean absolute change from baseline in LSS at Weeks 4, 8, 12, and 16
- Mean percentage change from baseline in PGA*BSA at Weeks 4, 8, 12, and 16
- Mean absolute change from baseline in PGA*BSA at Weeks 4, 8, 12, and 16
- Mean percentage change from baseline in DLQI score at Weeks 4, 8, 12, and 16 (main and sensitivity analysis)
- Mean absolute change from baseline in DLQI score at Weeks 4, 8, 12, and 16 (main and sensitivity analysis)
- Mean percentage change from baseline in mNAPSI total score at Weeks 4, 8, 12, and 16
- Mean absolute change from baseline in mNAPSI total score at Weeks 4, 8, 12, and 16

For the secondary endpoints the probability of each active treatment difference to placebo being less than 0 only will be presented.

Note that for the mNAPSI, only participants with psoriatic nail involvement (mNAPSI score>0) will be included in the summaries and analyses for this endpoint.

Similarly, if a participant has a zero score for any of the secondary scores at baseline, that participant will be excluded from any of the percentage change from baseline summaries and analyses as the percentage change from baseline cannot be calculated.

As described in [Section 9.2](#), any baseline covariates fitted into the primary analysis model will also be fitted in the models for these endpoints.

9.5.3 Response Endpoints with Inferential Analysis

The following endpoints will be analysed in the same manner as described below:

- Achievement of PASI-50 at Weeks 4, 8, 12 and 16
- Achievement of PGA of 0 or 1 with a ≥ 2 point improvement from baseline at Week 16
- Achievement of PGA of 0 at Week 16

9.5.3.1 Estimands

The population summary measure of interest will be the odds ratio between each active dose and placebo for the achievement of response at the relevant time point.

9.5.3.2 Main Analytical Approach

A generalised linear mixed effects model with a logit link function will be fitted using data from all visits. Treatment, visit and baseline score terms will be included in the model as fixed effects

together with treatment*visit and baseline score*visit interactions, where the baseline score of PASI or PGA is used as appropriate to the endpoint.

Treatment will consist of 4 levels (all placebo, EDP1815 1 capsule, EDP1815 4 capsules and EDP1815 10 capsules) if the placebo pooling strategy is considered appropriate or 6 levels (Placebo 1 capsule, Placebo 4 capsules, Placebo 10 capsules, EDP1815 1 capsule, EDP1815 4 capsules, and EDP1815 10 capsules) if the placebo pooling strategy is not considered appropriate. Visit will consist of 5 levels (Weeks 4, 8, 12,16 and 20).

As described in [Section 9.2](#), any baseline covariates fitted into the primary analysis model will also be fitted in the models for these endpoints.

An unstructured covariance structure will be used. If there are issues with model convergence, other covariance structures may be considered (e.g. compound symmetry).

If the assumption of similarity between the 3 placebo cohorts is considered appropriate, the placebo cohorts will be pooled, and a common all placebo control group will be used for the pairwise differences or each active dose to placebo. If the placebo pooling strategy is not considered appropriate, each placebo dose will be included in the model as a separate dose level and pairwise comparisons between each active EDP1815 dose and its matching placebo dose will be used.

If responder numbers are low and there are visits at which not all treatment groups have at least one response, the analysis may be modified to exclude one or more of the earlier visits and/or the Week 20 visit to ensure model convergence. Alternatively, the mixed effects model may be replaced with an individual logistic regression models at Week 16 or the baseline*visit interaction may be replaced by a fixed baseline effect only if either of these approaches appear to be more appropriate for the available data. Note that if there are insufficient responders to run the model with the Week 16 visit included then no inferential analysis should be performed.

The number and percentage of responders will be reported at each visit together with 95% CI for the percentage of responders, calculated using the exact method for binomial proportions. At each visit, the adjusted odds ratio, with 95% confidence interval (CI) associated p-value will also be presented. If the analysis is changed to exclude visits, then only the summary statistics for the number of subjects with data, the number and percentage of participants with a response and the 95% CI for the percentage of responders will be shown for any visits which were excluded from the model. Table footnotes will be added as appropriate to detail any changes to the planned analysis.

The adjusted odds ratios (with 95% CI) will be plotted by visit for the 3 active doses compared to placebo.

In addition, for the PASI-50 response endpoint only, a supportive analysis will be performed using the following supportive estimand. The estimand will differ only in the intercurrent event strategy.

Table 5 Intercurrent Event Strategy for Secondary Supportive Estimand for PASI-50

Estimand	Purpose	Population	Intercurrent Event Strategy
Secondary Supportive Estimand 1	Assess the impact of treatment discontinuation due to requirement for alternative therapy	miITT	Protocol deviation with potential to impact efficacy Treatment policy (as per Secondary estimand) Treatment discontinuation due to requirement for alternative therapy before Week 16 Composite (PASI-50 will be considered as not achieved at all scheduled visits after treatment discontinuation) Treatment discontinuation for any other reason before Week 16 While on treatment (as per Primary estimand)

9.5.3.3 Sensitivity Analyses

For the PASI-50, individually at each of Weeks 4, 8, 12, 16 and 20, and for the two endpoints for PGA score at Week 16, a Bayesian logistic regression will be performed. The model will include parameters for treatment and baseline PASI score.

Treatment will consist of 4 levels or 6 levels based on the appropriateness of the placebo pooling strategy as per the main analytical approach. As described in [Section 9.2](#), any baseline covariates fitted into the primary analysis model will also be fitted in the models for these endpoints.

The priors for all parameters in the model will be non-informative and follow a normal distribution with mean 0 and SD 1000.

100,000 MCMC samples will be generated with a thin of 20 to leave 5000 retained samples after a burn-in of 10,000 samples. The number of samples or thin may be increased to reduce the ratio of the Monte Carlo standard error (MCSE) to the posterior SD, as deemed necessary.

The posterior mean odds-ratios for each pairwise comparison of an active EDP1815 dose and placebo with associated 95% HPD CrI will be presented together with the posterior probability that the true odds ratio >1.

9.5.4 PASI-75, PASI-90 and PASI-100 at Week 16

The number and percentage of participants who achieve PASI-75 will be summarised by visit. Exact 95% CIs for the percentage of participants will also be displayed at each visit.

PASI-90 and PASI-100 will be summarised in the same manner.

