For the PASI-50, a generalized linear mixed effects model with a logit link function will be fitted using data from all visits. Treatment, visit, and baseline PASI score terms will be included in the model as fixed effects, together with treatment*visit and baseline PASI score*visit interactions, and any baseline covariates selected in the primary analysis model for the primary estimand. Odds ratios and 95% CIs for each active dose compared to placebo at each visit will be presented.

A supportive analysis for the PASI-50 will also be performed, in the same manner as described above, in which participants who withdraw from study drug before Week 16 due to requirement for alternative therapy will be included in the model with the PASI-50 endpoint imputed as ‘not achieved’ at all expected visits after study drug withdrawal.

A sensitivity analysis will also be performed on the PASI-50. Bayesian logistic regression models will be individually fitted at each of Weeks 4, 8, 12, and 16. The model will include parameters for treatment and baseline PASI score together with any baseline covariates selected in the primary analysis model for the primary estimand. The posterior odds-ratios for each pairwise comparison of an active EDP1815 dose and placebo with associated 95% HDP CrI will be presented together with the posterior probability that the true odds ratio >1.

Percentage of participants achieving PGA of 0 or 1 with a ≥ 2 -point improvement and percentage of participants achieving a PGA of 0 will be analyzed in the same manner as described above for PASI-50 with the exception that the sensitivity analysis using the Bayesian logistic regression model will only be fitted on the Week 16 data.

For the time to first achievement of PASI-50, a nonparametric survival analysis for interval censored data will be performed. The expectation-maximization iterative complex minorant (EMICM) method for iterative computation of the nonparametric maximum likelihood

estimator for the survival function (Wellner and Zahn 1997) will be used. The number and proportion of participants who meet the PASI-50 at least once during the study will be presented. A generalized log-rank test will be used to compare each active dose with placebo and the p-value for treatment difference will also be presented. The estimated survival curves for each treatment group will also be presented.

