7.2 Covariates and Subgroups

If the placebo groups from the 3 cohorts are found to be too heterogeneous to be pooled (see [Section 9.1](#)), the primary and secondary analyses will be performed using within-cohort comparisons of active and placebo treatments, and summary tables will also be produced by cohort.

Subgroups based on baseline severity of disease and obesity will be defined as follows:

- Using baseline PASI score ($<10, \geq 10$)
- Using baseline PGA score (2, 3)
- Using baseline BMI ($<30 \text{ kg/m}^2, \geq 30 \text{ kg/m}^2$)

For the exploratory analysis indirectly comparing the results from this study to those in the UNVEIL study ([Section 9.6.2](#)) the following subgroup of participants will be used:

- Baseline PGA=3 and Baseline BSA 5-10%

For the inferential models defined in [Section 9](#), in addition to the relevant baseline score where applicable, the following covariates will be considered:

- Body mass index (<30 kg/m², ≥30 kg/m²)
- Sex (male, female)
- Country (UK, Poland, Hungary, USA)
- Time since diagnosis (<2 years, ≥2 years)

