9.2 Selection of Additional Covariates

The covariates described in [Section 7.2](#) will be considered and included in the primary efficacy model described in [Section 9.4.3](#) for the primary estimand if found to be significant ($p<0.05$). A forward stepwise selection method will be used to include the covariates after the treatment*visit and baseline PASI score*visit interactions have already been fitted.

The covariates selected for this primary model will also be used in all other analytical models including covariates.

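### The Bayesian logistic sensitivity models for the two Week 16 PGA endpoints adjust for baseline PASI, while the main model they check uses the baseline score matched to the endpoint

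*SAP*

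**What the plan says.** SAP 9.5.3.3 covers PASI-50 at each of five visits, "and for the two endpoints for PGA score at Week 16, a Bayesian logistic regression will be performed". It then gives one specification for all of them: "The model will include parameters for treatment and baseline PASI score". It adds any covariates carried over from the primary model and makes no exception for PGA.

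SAP 9.5.3.2, the main analysis of the same endpoints, fits a generalised linear mixed model with a baseline score term, "where the baseline score of PASI or PGA is used as appropriate to the endpoint". SAP 7.2 takes the same general line for the inferential models: "in addition to the relevant baseline score where applicable, the following covariates will be considered". The candidates listed there are BMI, sex, country and time since diagnosis. SAP 9.2 selects among them in the primary PASI model only and then states: "The covariates selected for this primary model will also be used in all other analytical models including covariates".

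Protocol 7.6.2 differs from SAP 9.5.3.2. For the Bayesian PASI-50 model it says "The model will include parameters for treatment and baseline PASI score together with any baseline covariates". It carries the PASI-50 methods over to the PGA endpoints "with the exception that the sensitivity analysis using the Bayesian logistic regression model will only be fitted on the Week 16 data". No change of baseline score is mentioned. SAP Table 8, which lists changes from the protocol, has no entry on it.

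**The concern.** A sensitivity analysis is easiest to read when it varies one thing. For PASI-50 the baseline score is the same in both models. For the two PGA endpoints the baseline score changes as well. If the two results differ, the reader cannot tell whether the cause is the Bayesian single-visit method or the covariate.

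The covariate is not an arbitrary one. Both PGA endpoints are defined on the PGA scale, and entry restricts baseline PGA to 2 or 3, so the baseline category affects what counts as a response. Baseline PASI is an imperfect stand-in. PASI weights intensity by area affected in each body region (SAP Appendix 2), whereas PGA averages induration, erythema and scaling with no area term (SAP 5.3.3.5 and Appendix 3).

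The mismatch would be most visible under the SAP's own fallback. If responders are few, 9.5.3.2 allows the mixed model to be replaced by a logistic regression at Week 16. The main and sensitivity models would then be close to identical in structure and yet could adjust for different baseline scores.

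**Working it through.** The plan states no figure on this point, so there is none to reproduce. The check has three steps.

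**1. Does baseline PGA enter the response definitions?** Inputs: baseline PGA 2 or 3 (protocol 4.1.1, criterion 4) and the endpoint definitions in SAP 9.5.3. PGA is taken as the whole-number score.

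| Endpoint at Week 16 | Baseline 2 | Baseline 3 |
|---|---|---|
| PGA 0 or 1 with at least 2 points gained | must reach 0 (drop of 2) | may reach 0 or 1 (drop of at least 2) |
| PGA 0 | must reach 0 (drop of 2) | must reach 0 (drop of 3) |

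For the first endpoint the smallest qualifying drop is 2 points in both groups, and what differs is the end state that qualifies. For the second endpoint the end state is the same and the drop differs. Baseline PGA matters for both, in different ways.

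**2. Can baseline PGA enter the sensitivity model by another route?** The only additional covariates are those selected from the four candidates in SAP 7.2. Baseline PGA is not among them, so it cannot.

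**3. How large could the effect be?** The documents give no PGA response rates, so every rate below is an assumption. The calculation leaves out all baseline adjustment. The SAP model does adjust for baseline PASI, which would recover part of the adjustment to the extent that PASI and PGA are correlated.

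Assumed response, first endpoint: baseline 2, 5% active and 2% placebo; baseline 3, 24% active and 10% placebo.

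- Odds ratios (OR) by stratum: (0.05/0.95)/(0.02/0.98) = 2.58 and (0.24/0.76)/(0.10/0.90) = 2.84.
- Baseline 3 share 50% in both arms: active 0.145, placebo 0.060; OR = (0.145/0.855)/(0.060/0.940) = 2.66.
- 60% active, 50% placebo: active 0.6×0.24 + 0.4×0.05 = 0.164; OR = (0.164/0.836)/(0.060/0.940) = 3.07.
- 50% active, 60% placebo: placebo 0.6×0.10 + 0.4×0.02 = 0.068; OR = (0.145/0.855)/(0.068/0.932) = 2.32.

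How often such an imbalance occurs: SAP section 6 expects 42 active and 21 placebo participants per cohort at Week 16, hence 3×21 = 63 pooled placebo. At a 50% share the standard error of the difference is √[0.25×(1/42 + 1/63)] = 0.0996. A gap of 10 points or more has probability about 32% in either direction, or about 16% in one given direction.

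Comparison with sampling error, in the 60% v 50% case: SE(log OR) = √[1/(42×0.164×0.836) + 1/(63×0.060×0.940)] = 0.67, with about 7 active and 4 placebo responders. The 95% interval around 3.07 is roughly 0.8 to 11.5. The shift from 2.66 to 3.07 is ln(3.07/2.66) = 0.14, about 0.2 standard errors.

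Range under other assumptions: 20–50% of participants at baseline 2, placebo response of 10–20% at baseline 3, and an odds ratio of 0.1–0.5 for baseline 2 against 3. With balanced arms, a conditional treatment OR of 2.0 appears as 1.86–1.99 when baseline PGA is omitted, and 3.0 appears as 2.63–2.98. With 50 active and 75 placebo randomised, a one-standard-deviation imbalance (7–9 percentage points), placed in the active arm, moves a true 2.0 to between 1.56 and 2.24.

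**The case against.** The strongest reply is that SAP 9.5.3.3 does what the protocol says. Protocol 7.6.2 names baseline PASI and extends the approach to the PGA endpoints with a timing exception only. On that view 9.5.3.2 is the section that departs, and it does so without an entry in Table 8. This stands as a matter of record, and it means the fix must include Table 8. It does not explain why the SAP adopts the matched score in one section, and refers to the relevant score in 7.2, but not in the section that checks the result.

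The second reply is that little depends on it. These are sensitivity analyses of secondary endpoints, protocol 7.6.2 treats the secondary results as descriptive, the main PGA model already uses baseline PGA, and no decision rule draws on this output. All of that stands and limits the weight of the point.

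The third reply is that the two analyses already differ by design: one is an all-visit frequentist mixed model, the other a single-visit Bayesian model. Their odds ratios need not agree even with the same covariate. A reader might infer that the mismatch makes the two analyses incomparable, and that goes too far. What remains is that an avoidable second difference has been added.

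**Conclusion.** The inconsistency is real, and nothing else in the plan repairs it. For both PGA endpoints the sensitivity model changes the baseline covariate as well as the inference method, and it adjusts only partly for chance imbalance in baseline PGA.

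Three stronger readings are tempting, and the documents do not support them:

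- A reader might infer that baseline PGA determines how far a participant must improve. That holds only for PGA 0. For the other endpoint both groups need at least 2 points.
- A reader might infer that baseline PGA is the strongest prognostic factor. No section gives response rates or ranks predictors; a place in the response definition does not establish prognostic strength.
- A reader might infer that the treatment effect would be inflated. The shift can go either way: about 2.7 becomes 3.1 or 2.3 depending on the direction of a 10-point imbalance.

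The size rests on assumed rates for one endpoint and on no baseline adjustment, which overstates the effect to the extent that baseline PASI stands in for baseline PGA. Even so, the shift is small beside the standard error. This is a minor, cost-free improvement and does not threaten any conclusion of the trial.

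**What to change.** In SAP 9.5.3.3, specify treatment and the baseline score that matches the endpoint: baseline PASI for PASI-50 and baseline PGA for both PGA endpoints, as 9.5.3.2 already does. In SAP Table 8, record the endpoint-matched baseline score, for 9.5.3.2 and 9.5.3.3 together, as a change from protocol 7.6.2. If baseline PASI was intended for the PGA sensitivity models, say so and give the reason.

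The cost is one sentence and one table row. Baseline PGA is already collected, and sample size, data collection and trial conduct do not change.

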The primary efficacy endpoint is the percent change from baseline in the PASI score at Week 16. Percent change from baseline relative to placebo will be estimated within the model ([Section 9.4.3](#)) as (percent change in active) - (percent change in placebo), with a negative value indicating a greater improvement for active than placebo. A percent change from baseline relative to placebo of at least 20% will be considered clinically meaningful. The pooled standard deviation across all doses is assumed to be 25%.

Participants in the placebo arm of each cohort will be pooled for the statistical analysis in order to compare active and control arms resulting in 75 participants randomized to the pooled placebo group and 50 participants randomized to each active treatment group (EDP1815 0.8 \times 10¹¹ cells, EDP1815 3.2 \times 10¹¹ cells, and EDP1815 8.0 \times 10¹¹ cells). Assuming that no more than 15% of

participants will discontinue treatment before the Week 16 visit, at least 42 active and 21 placebo participants in each of the 3 cohorts are expected to provide data through the Week 16 visit.

Each pairwise comparison between pooled placebo and active dose would be expected to have more than 95% power to detect a difference between the treatment groups at the 5% significance level under the assumption that pooling the placebo groups is a valid strategy. If the 3 placebo cohorts are considered too heterogeneous for pooling into a single reference group ([Section 9.1](#)), the power to detect a difference in each within-cohort pairwise comparison between active and placebo doses would be greater than 80%.

As the statistical inference for this study will focus on estimation rather than testing a formal hypothesis, no multiplicity adjustments of the different comparisons between groups in order to control the study-wise type I error rate will be performed.

Similarly, as there is no intention to use any interim analyses to stop the study early for efficacy ([Section 7.4](#)), no adjustments for multiplicity will be made to account for any analyses performed as part of the interim analyses.

7 General Considerations

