14.2.1.5.2	Summary of Percentage Change from Baseline in PASI Score by Baseline PGA Category Primary Estimand	miITT		
14.2.1.5.3	Summary of Percentage Change from Baseline in PASI Score by Baseline BMI Category Primary Estimand	miITT		
14.2.1.6.1	Analysis of Percentage Change from Baseline in PASI Score by Baseline PASI Category - Bayesian MMRM Primary Estimand	miITT		
14.2.1.6.2	Analysis of Percentage Change from Baseline in PASI Score by Baseline PGA Category - Bayesian MMRM Primary Estimand	miITT		
14.2.1.6.3	Analysis of Percentage Change from Baseline in PASI Score by Baseline BMI Category - Bayesian MMRM Primary Estimand	miITT		
14.2.2.1	Summary of Change from Baseline in PASI Score	miITT	Y	
14.2.2.2	Analysis of Change from Baseline in PASI Score - Bayesian MMRM	miITT	Y	
14.2.3.1.1	Summary and Analysis of PASI-50 Response - GLMM	miITT	Y	
14.2.3.1.2	Summary and Analysis of PASI-50 Response - GLMM Secondary Supportive Estimand 1	miITT		
14.2.3.2	Analysis of PASI-50 Response - Bayesian Logistic by Visit	miITT		
14.2.4	Summary and Analysis of Time to First Achievement of PASI-50	miITT		
14.2.5	Summary of PASI-75 Response	miITT	Y	
14.2.6	Summary of PASI-90 Response	miITT	Y	
14.2.7	Summary of PASI-100 Response	miITT	Y	
14.2.8.1	Summary and Analysis of PGA of 0 or 1 With a ≥ 2 Point Improvement from Baseline Response - GLMM	miITT	Y	

Number	Title	Population	Interim	Programming notes
14.2.8.2	Analysis of PGA of 0 or 1 With a >=2 Point Improvement from Baseline Response - Bayesian Logistic at Week 16	miITT		
14.2.9.1	Summary and Analysis of PGA of 0 Response - GLMM	miITT	Y	
14.2.9.2	Analysis of PGA of 0 Response - Bayesian Logistic at Week 16	miITT		
14.2.9.3	Summary of PGA of 0 or 1 Response	miITT		
14.2.10.1	Summary of Percentage Change from Baseline in PGA*BSA	miITT	Y	
14.2.10.2	Analysis of Percentage Change from Baseline in PGA*BSA - Bayesian MMRM	miITT		
14.2.11.1	Summary of Change from Baseline in PGA*BSA	miITT	Y	
14.2.11.2	Analysis of Change from Baseline in PGA*BSA - Bayesian MMRM	miITT		
14.2.12.1	Summary of Percentage Change from Baseline in LSS	miITT		
14.2.12.2	Analysis of Percentage Change from Baseline in LSS - Bayesian MMRM	miITT		
14.2.13.1	Summary of Change from Baseline in LSS	miITT		
14.2.13.2	Analysis of Change from Baseline in LSS - Bayesian MMRM	miITT		
14.2.14.1.1	Summary of Percentage Change from Baseline in DLQI Score Main Analysis	miITT		

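### The Bayesian logistic sensitivity analyses report a posterior mean odds ratio under SD 1000 priors, which overstates the odds ratio in the data when placebo responders are few

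*SAP*

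**What the plan says.** SAP 9.5.3.3 plans Bayesian logistic regressions for PASI-50, separately at Weeks 4, 8, 12, 16 and 20, and "for the two endpoints for PGA score at Week 16, a Bayesian logistic regression will be performed". PGA 0 is one of the two PGA endpoints and has its own output, Table 14.2.9.2: "Analysis of PGA of 0 Response - Bayesian Logistic at Week 16".

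The prior is stated as follows: "The priors for all parameters in the model will be non-informative and follow a normal distribution with mean 0 and SD 1000". In a logistic model these parameters are on the log-odds scale. The planned point estimate is "The posterior mean odds-ratios for each pairwise comparison of an active EDP1815 dose and placebo", reported with a 95% HPD credible interval and the posterior probability that the odds ratio exceeds 1. On computation: "100,000 MCMC samples will be generated with a thin of 20 to leave 5000 retained samples after a burn-in of 10,000 samples". More samples or thinning are allowed if Monte Carlo error is too large.

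Protocol 7.6.2 speaks only of posterior odds ratios with a 95% high-density interval. The choice of the mean is therefore the SAP's own.

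Three other places matter:
- SAP Section 6 gives the group sizes: "75 participants randomized to the pooled placebo group and 50 participants randomized to each active treatment group", and after dropout "at least 42 active and 21 placebo participants in each of the 3 cohorts are expected to provide data through the Week 16 visit".
- SAP 9.5.3.2, for the main mixed model, lets visits be dropped or the model simplified when responders are few. It calls for no inference if there are too few to fit the model with Week 16 included.
- SAP Section 12 requires production and QC runs, which use different seeds, to agree on odds ratios within 5% or 0.1.

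**The concern.** An odds ratio has a skewed posterior, and the skew grows as the placebo responder count falls. Its mean is then governed by draws in which the placebo response rate is close to zero. An SD of 1000 on the log-odds scale does nothing to limit those draws. The median is not affected in this way.

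The distortion is upward. Where placebo responders are few, the sensitivity table could show an odds ratio well above the one in the data only because of the summary chosen. A sensitivity analysis is meant to show whether the mixed-model result is robust, and it cannot do so if its summary can double the estimate.

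**Working it through.** **Group sizes.** The SAP states no figure for the logistic analyses, so I first reproduced the power statement that rests on the same sizes. Retention of 85% gives 0.85 × 50 = 42.5 and 0.85 × 25 = 21.25, hence 42 active and 21 placebo per cohort, and 3 × 21 = 63 pooled placebo. The effect is 20 points ("A percent change from baseline relative to placebo of at least 20% will be considered clinically meaningful"), the SD is 25, and I took the 5% level as two-sided.
- Pooled: SE = 25 × √(1/42 + 1/63) = 4.98; 20/4.98 − 1.96 = 2.06; power 98.0%. The SAP says more than 95%.
- Within cohort: SE = 25 × √(1/42 + 1/21) = 6.68; 20/6.68 − 1.96 = 1.03; power 84.9%. The SAP says greater than 80%.

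The sizes are consistent with the stated power.

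**Mean odds ratio.** I used an unadjusted two-group model with x1 of n1 active and x0 of n0 placebo responders, and independent, essentially flat priors on each logit. The posteriors are Beta(x, n−x), so

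E[OR] = [x1/(n1−x1−1)] × [(n0−x0)/(x0−1)], for x0 ≥ 2.

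Numerical integration with the actual SD 1000 prior gives the same values when x0 ≥ 2. Dividing by the crude odds ratio gives

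E[OR]/crude = [(n1−x1)/(n1−x1−1)] × [x0/(x0−1)].

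The first factor is close to 1 (38/37 = 1.03 for 4/42), so the inflation is roughly x0/(x0−1) and hardly depends on group size.

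| Active v placebo | Mean | Crude | Median |
|---|---|---|---|
| 4/42 v 2/63 | (4/37) × (61/1) = 6.59 | 3.21 | 3.54 |
| 5/42 v 3/63 | (5/36) × (60/2) = 4.17 | 2.70 | 2.85 |
| 2/42 v 3/63 (equal rates) | (2/39) × (60/2) = 1.54 | 1.00 | 0.94 |
| 10/42 v 8/63 | (10/31) × (55/7) = 2.53 | 2.15 | 2.18 |

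**One or no placebo responder.** The closed form no longer applies, so I integrated under the SD 1000 prior with 4/42 active.
- One responder: the mean is about 8,370, against a crude 6.5 and a median of 8.7. The exact value depends on how the model is parameterised. A flat-prior HPD interval on the odds-ratio scale runs from about 0.10 to 130, so the mean lies outside its own interval.
- No responder: about 48% of draws overflow double precision. The median fails as well, with a median log odds ratio of about 680.

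**Stability against the QC tolerance.** I used 5000 independent draws and 200 seeds, with 4/42 active. The mean meets the tolerance in about 7% of seed pairs at one placebo responder, 69% at two and 96% at three. The median does so in 90%, 96% and 98%.

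**How often placebo responders would be this few.** No placebo rate is given for any binary endpoint, so the rates below are assumptions. P(X ≤ 1) = (1−p)^n + n·p·(1−p)^(n−1).

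| Assumed placebo rate | 1% | 2% | 3% | 5% | 10% |
|---|---|---|---|---|---|
| Pooled, n = 63 | 87% | 64% | 43% | 17% | 1% |
| Not pooled, n = 21 | 98% | 93% | 87% | 72% | 36% |

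**The case against.** Several points on the other side stand.

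- A reader might infer that the mean is infinite or does not exist. That is true only in the flat-prior limit. The SAP's normal prior is proper, so the mean is finite, although useless at one or no placebo responder.
- A reader might infer that very few placebo responders are to be expected for PGA 0. Neither document gives a rate. SAP 9.5.3.2 allows for low responder numbers in general, but that is not a forecast for any endpoint. At an assumed 10% rate the pooled problem of one or no responder almost disappears.
- A reader might infer that the PGA 0/1 and early PASI-50 odds ratios would be badly overstated too. That depends on their placebo counts. At 8 placebo responders the inflation is 2.53/2.15, about 18%.
- The plan has some protection. The no-inference rule in SAP 9.5.3.2 could be read across and might suppress the zero-responder case. The QC tolerance would usually catch the wild values at one responder.
- The stakes are limited. These are sensitivity analyses of secondary endpoints, and protocol 7.6.2 treats such results as descriptive. The three tables (14.2.3.2, 14.2.8.2, 14.2.9.2) are not marked for the interim analysis. The mixed-model results appear with responder counts and exact intervals, so sparse data would be visible.

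The protections do not settle the matter. The 9.5.3.2 rule is written for the mixed model and sets no minimum count. Its trigger is inability to fit, yet a Bayesian model with a proper prior can be run even with no responders. It does not clearly cover one to three responders. The QC check tests agreement between seeds, so two runs can agree on the same inflated mean: at three responders 96% of pairs pass while the mean is about 1.5 times the crude value. Drawing more samples does not change the quantity being estimated.

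**Conclusion.** The point holds as a reporting weakness with a known size. The posterior mean odds ratio in SAP 9.5.3.3 is about twice the crude value at two placebo responders, about 1.5 times at three and about 1.2 times at eight. At one or none it is not usable. Even with equal observed rates (2/42 v 3/63) it would report 1.54.

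This rests on an unadjusted model; the planned one also includes baseline PASI and any selected covariates. It uses the SAP's minimum Week 16 numbers; earlier visits should have more participants, but the inflation depends mainly on the placebo responder count. It also takes the SAP to mean the average of the odds ratio itself. If the exponentiated mean log odds ratio was intended, the inflation largely goes (3.71 rather than 6.59 for 4/42 v 2/63), and the SAP should say so.

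The documents do not support a claim that these tables will mislead: that depends on placebo rates they do not give. P(OR>1) does not depend on whether the mean or the median is shown, and no decision rule uses the odds ratio. It should be changed because the remedy is nearly free, but it does not threaten the trial's main conclusions.

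**What to change.** In SAP 9.5.3.3:

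1. Report the posterior median odds ratio in place of the mean, and keep P(OR>1).
2. Compute the 95% HPD interval on the log odds ratio and exponentiate it. This keeps the interval type named in protocol 7.6.2. An equal-tailed interval is also reasonable, but should be listed in SAP Section 13 as a change from the protocol.
3. Deal with sparse endpoints explicitly, since the median also fails at zero placebo responders under SD 1000. Either state a weakly informative prior for the log odds ratios, for example Normal(0, SD 2.5), or extend the no-inference rule of 9.5.3.2 to this analysis whenever a compared group has no responders.

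Changing the prior while keeping the mean is not enough. With an SD 2.5 prior on each group's logit, the mean for 4/42 v 2/63 is still 4.4, against a crude 3.2.

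The cost is a few sentences in the SAP and small programming changes, with no new data. The downside of the tighter prior is mild shrinkage of extreme odds ratios. SD 2.5 is one possible choice, and whichever is used should be fixed before unblinding.
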